7.4. Data Sources

Data will be obtained retrospectively from the IMDC clinical sites.

The IMDC cohort is a multi-institutional cohort that collects data globally from 35 international cancer centers in the United States, Canada, Denmark, Greece, South Korea, Australia, New Zealand, Japan, Singapore, Italy, and Belgium. Demographic, clinical, laboratory, and outcome data on patients with mRCC are collected retrospectively from medical charts using uniform database templates and standardized definitions to ensure data are collected consistently. Medical records include longitudinal information on patient demographic and disease characteristics, oncology-specific workups and evaluations, treatment types and duration, concurrent diagnoses as documented in physician notes, and treatment discontinuation/halt decisions.

AGI will collaborate with [name] from the PPD who will serve as the principal investigator for this study and who is also the Chair of the IMDC, to obtain data from clinical centers. The clinical centers send data to the IMDC database, which is updated frequently (ie, quarterly or continuously). Data cleaning and consolidation of the data occur twice a year.

For this proposed study, a "limited" dataset of first-line sunitinib patients will be provided. The "limited" dataset will be anonymized and will not contain any personal data. All first-line sunitinib patients are included in the "limited" dataset, but only a select number of variables necessary to fulfill the study objectives will be included.

7.5. Study Size

The IMDC database has approximately 7,000 mRCC patients who received sunitinib at any line of treatment. About 2,000-3,000 patients received first-line sunitinib. Power calculation was not performed as the main objectives were descriptive.

7.6. Data Management

AGI will work with the IMDC data manager and [name] to understand all available data elements from the IMDC database.

Once study site contracts have been completed, the most recent data will be transferred to AGI over a secured network to ensure that the latest available data are used in the analysis. Data provided to AGI will be anonymized and will not contain any personal data. After obtaining the data, AGI will assess the quality of the data downloaded and work with data managers from each center to rectify any potential data entry errors and discrepancies.

7.7. Data Analysis

Identification of the Study Cohort

The study population of interest in the current study are patients treated with first-line sunitinib. Each patient's eligibility for study will be verified against the eligibility criteria.

Description of patient demographic and clinical characteristics among patients in the study cohort, stratified by IMDC prognostic risk group

Baseline demographic and clinical characteristics prior to the index date will be described using the mean (standard deviation [SD]) and median values for continuous variables and frequency distributions for categorical variables. Demographic and clinical characteristics will also be summarized, stratified by IMDC prognostic risk groups (ie, favorable, intermediate, and poor). Comparisons will be performed using chi-square tests or Fisher's exact test, as appropriate, for categorical variables and Wilcoxon-Mann-Whitney non-parametric tests for continuous variables.

Characterization of clinical outcomes of mRCC patients treated with first-line sunitinib

The following clinical outcomes will be stratified by IMDC prognostic risk groups (ie, favorable, intermediate, and poor) and KPS (eg, 0-40%, 50-70%, and 80-100%).

- OS and TTD will be analyzed using Kaplan-Meier estimator.
- Reasons for first-line sunitinib therapy discontinuation will be described using relative frequencies.
- Physician-assessed best tumor response (ie, objective response rate, stable disease, and progressive disease) to first-line sunitinib will be described using relative frequencies.

Indirect qualitative evaluation of the real-world clinical outcomes of mRCC patients treated with first-line sunitinib with that of phase II and III clinical trials

An indirect qualitative, side-by-side evaluation of clinical outcomes will be conducted between the following groups:

• Previously untreated sunitinib patients with intermediate or poor IMDC risk score from the real-world IMDC database *vs* previously untreated sunitinib patients with intermediate or poor IMDC risk score from the 1) CABOSUN trial, 2) CheckMate 214, and 3) sunitinib vs. IFN-α trial.

Subgroup analysis describing demographic and clinical characteristics and characterizing clinical outcomes among patients in the IMDC intermediate risk group, stratified by patients having only 1 vs 2 risk factors

• Among patients identified as having intermediate IMDC risk score (defined as having 1 or 2 IMDC risk factors), a subgroup analysis will assess baseline demographic and clinical characteristics, distribution of individual IMDC risk factors, and clinical outcomes (ie, OS, TTD, and ORR), stratified by patients having only 1 risk factor vs. 2 risk factors. Demographic and clinical characteristics and clinical outcomes (ie, OS, TTD, and ORR) will be analyzed using the same methodology applied in the full study cohort. Absolute and relative frequency of each IMDC factor within the intermediate risk group will be reported.

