4. MILESTONES

Milestone	Planned date	
Start of data collection	July 2018	
End of data collection	September 2018	
For studies with primary data collection, enter the planned		
date for last subject last visit (LSLV). For studies with		
secondary data collection, enter the planned date on which		
the analytical dataset will be first completely available; the		
analytic dataset is the minimum set of data required to		
perform the statistical analysis for the primary objective(s).		
Final study report	January 2019	
Enter the planned date for approval of final study report.		
For NI PASS protocols, the final study report must be		
submitted within 12 months of the end of data collection.		

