Findings from the CABOSUN trial showed that patients (IMDC intermediate and poor risk) taking sunitinib had a PFS of 5.6 months. This was lower than the results from a phase III trial that examined sunitinib versus interferon alfa in untreated clear cell mRCC patients where the PFS was 11.0 months in the sunitinib group vs. 5.0 months in the interferon alfa group. A recent retrospective analysis of the phase III trial demonstrated that, of the 373 patients treated with sunitinib, there were 36% favorable, 55% intermediate, and 9% poor based on the IMDC prognostic risk group. In addition, the median PFS for patients treated with sunitinib was 14.1 months (95% CI: 13.4, 17.1), 10.7 months (95% CI: 10.5, 12.5), and 2.4 months (95% CI: 1.1, 4.7) for favorable, intermediate, and poor risk groups, respectively. When intermediate and poor IMDC risk groups were combined. the median PFS was 10.6 months (95% CI: 8.1, 10.9). 10 CheckMate 214 was another phase III trial that compared nivolumab plus ipilimumab (nivo+ipi) with sunitinib for previously untreated clear cell mRCC. The results from this trial showed that among patients in the intermediate and poor IMDC risk groups, the median PFS was 11.6 months (95% CI: 8.7, 15.5) in the nivo+ipi vs. 8.4 months (95% CI: 7.0, 10.8) in the sunitinib. Of the 426 patients in the intermediate and poor risk groups, 334 (79%) and 91 (21%) patients were identified as intermediate and poor risk, respectively. 11 Based on the differences in PFS between these studies, patient IMDC prognostic risk group may play a role in the effect of first-line treatment on clinical outcomes.

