7. RESEARCH METHODS

7.1. Study Design

This is a retrospective, longitudinal cohort study that involves the analysis of retrospective data collected through the IMDC database. A cohort of mRCC patients who initiated sunitinib as first-line therapy will be evaluated.

The index date will be defined as the date of initiation of first-line sunitinib therapy. The baseline period will be defined as the time from mRCC diagnosis to the index date. The follow-up period will be defined as the time from the index date to the earliest of death or end of data availability. Figure 1 depicts the study design scheme.

Figure 1. Study Design Scheme

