7.2.2. Exclusion Criteria

- Initiated first-line sunitinib treatment before 2010;
- Had non-clear cell mRCC.

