7.3. Variables

Primary exposure

• Sunitinib as first-line therapy.

Outcomes

- OS, defined as the time between index date and death.
- TTD, defined as the time between index date and discontinuation of therapy due to any reason including progression, death, or toxicity.
- Reasons for treatment discontinuation, categorized as progression, death, toxicity, or other.
- Physician-assessed best response, defined as ORR (sum of partial response and complete response), progressive disease, and stable disease.

Covariates (assessed during the baseline period or at index date).

- Gender.
- Age at time of mRCC diagnosis.
- Race.
- Date of RCC diagnosis.
- Date of mRCC diagnosis.
- Prior nephrectomy.
- Date of nephrectomy (if applicable).
- Pathology.
 - Non clear cell RCC.
 - Clear cell RCC.
- Number of metastatic sites (eg., 1 site or more than 1 site).
- Site of metastases (eg, brain metastasis).
- IMDC prognostic risk factors.
 - Time from diagnosis to treatment initiation.
 - Karnofsky performance status at index date.
 - Serum hemoglobin at index date.

- Serum corrected calcium at index date.
- Neutrophil count (absolute count) at index date.
- Platelet count at index date.

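### Reasons for stopping sunitinib are tabulated with no stated denominator and no allowance for patients still on drug, so figures by risk group can carry a modest follow-up artefact

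*Combined protocol and SAP*

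**What the plan says.** Section 7.3 defines TTD as the time to stopping for any cause, and lists a companion outcome: "Reasons for treatment discontinuation, categorized as progression, death, toxicity, or other". There is no category for patients who have not stopped.

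In Section 7.7, "The following clinical outcomes will be stratified by IMDC prognostic risk groups (ie, favorable, intermediate, and poor) and KPS". Two neighbouring bullets then treat linked outcomes differently. For the time: "OS and TTD will be analyzed using Kaplan-Meier estimator". For the reasons: "Reasons for first-line sunitinib therapy discontinuation will be described using relative frequencies". No denominator, time horizon or rule for patients still on sunitinib is given for the reasons.

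Section 7.1 sets no minimum follow-up: "The follow-up period will be defined as the time from the index date to the earliest of death or end of data availability". Section 7.2.2 excludes patients who "Initiated first-line sunitinib treatment before 2010", and Section 4 puts the end of data collection at "September 2018". The limitations in Section 7.8 do not mention censoring of the reasons.

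**The concern.** Progression, death, toxicity and other are mutually exclusive ways of reaching the one TTD event. A patient still on sunitinib at the cut has a censored TTD and no reason yet. Kaplan-Meier allows for that patient; a simple percentage does not.

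The share of such patients should differ by risk group, because time on drug does. Section 5 presents the study as a source of contemporary real-world benchmarks and Section 7.7 reports the reasons by stratum, so readers will compare the columns. Part of any difference they see could come from unequal completeness of follow-up, and without a stated denominator they could not tell which way it acts.

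**Working it through.** The plan gives no figure to reproduce, so the check asks how large the effect could be.

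**Inputs from the documents**
- Median PFS on sunitinib by IMDC group (Section 5): "the median PFS for patients treated with sunitinib was 14.1 months (95% CI: 13.4, 17.1), 10.7 months (95% CI: 10.5, 12.5), and 2.4 months" for favorable, intermediate and poor risk.
- Starts from January 2010 and data to mid-September 2018 (Sections 7.2.2 and 4): T = 8 × 12 + 8.5 = 104.5 months.

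**Assumptions, not in the documents**
- Median PFS stands in for median TTD.
- Time on drug is exponential.
- Starts are uniform over the window.
- There is no loss to follow-up.

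**Step 1. Share still on drug at the cut**

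With λ = ln 2 / median, the share is (1 − e^(−λT)) / (λT). If starts ended in December 2016 (84 months of starts, at least 20.5 months of follow-up), it is (e^(−20.5λ) − e^(−104.5λ)) / (84λ).

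| Group | λ | λT | Starts to the cut | Starts to Dec 2016 |
|---|---|---|---|---|
| Favorable | 0.0492 | 5.137 | (1 − 0.0059)/5.137 = 19.4% | (0.3650 − 0.0059)/4.129 = 8.7% |
| Intermediate | 0.0648 | 6.770 | (1 − 0.0011)/6.770 = 14.8% | (0.2650 − 0.0011)/5.442 = 4.8% |
| Poor | 0.2888 | 30.18 | 1/30.18 = 3.3% | 0.0027/24.26 = 0.01% |

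**Step 2. All patients as denominator**

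Suppose every group has the same eventual mix of reasons, constant over time. The reported figure is then the eventual share × (1 − share on drug).

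| Eventual share (illustrative) | Favorable | Intermediate | Poor |
|---|---|---|---|
| 15%, starts to the cut | 12.1% | 12.8% | 14.5% |
| 70%, starts to the cut | 56.5% | 59.7% | 67.7% |
| 70%, starts to Dec 2016 | 63.9% | 66.6% | 70.0% |

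A reason that eventually accounts for 70% of stops in every group shows a favorable-to-poor gap of 67.7 − 56.5 = 11.2 points, or 70.0 − 63.9 = 6.1 points with the earlier end of starts. If the mix changes with time, the understatement is smaller for early reasons and larger for late ones, but the total missing is still the share on drug.

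**Step 3. Discontinuers only as denominator**

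Let the hazard of all other reasons be b, and the toxicity hazard be m·a up to month w and a afterwards, with a/(a + b) = 15%. Solve for b so that each group keeps its median. With S(t) the probability of still being on drug at t, and G(t) = (T − t)/T the chance that follow-up reaches t, the observed toxicity share is ∫h_tox·S·G / ∫h_all·S·G. The eventual share is the same ratio without G. The 15%, m and w are assumptions. Excess of observed over eventual toxicity share, in points, with starts to the cut:

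| Toxicity pattern | Favorable | Intermediate | Poor |
|---|---|---|---|
| Constant mix (m = 1) | 0 | 0 | 0 |
| m = 3, first 3 months | +0.7 | +0.7 | +0.3 |
| m = 6, first 3 months | +1.7 | +1.5 | +0.7 |
| m = 3, first 6 months | +1.2 | +1.1 | +0.2 |
| m = 6, first 6 months | +2.9 | +2.5 | +0.5 |

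The favorable-minus-poor contrast moves by 0 to about 2.4 points (2.9 − 0.5). If starts ended in December 2016, the largest excesses fall to +1.6, +1.2 and 0.0, with G(t) = min(1, (104.5 − t)/84). KPS strata cannot be checked in this way, because the documents give no time on drug by KPS.

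**The case against.** The strongest reply is that the table answers a legitimate descriptive question: among those who stopped, why did they stop? Section 7.5 calls the main objectives descriptive. The chi-square and Fisher tests in Section 7.7 are placed under baseline characteristics, and no test or effect measure is planned for reasons. Kaplan-Meier TTD by the same strata already shows how many remain on drug. With discontinuers as denominator, bias relative to the eventual mix requires that mix to change with time on drug, and the documents give no data on timing. Uniform starts right up to the cut also maximise recent starters compared with an earlier end of starts.

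Most of this stands, and it limits the point to a modest one. It does not remove it. The plan does not say that discontinuers are the denominator, and with all patients the artefact needs no timing assumption. Raw counts can answer the question about those who stopped, provided the table says that this is what it shows.

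A reader might go further and infer that favorable-risk patients will falsely appear to stop for toxicity markedly more often, by 5 points or more. The documents do not support that. The direction presupposes a denominator of discontinuers, and a shift of that size did not arise under starts spread over 2010 to 2018. With a 3-month early window it appears only when starts are concentrated near the cut: if all fell in the last 24 months, the excess at m = 6 would be +8.8, +8.1 and +3.5 points. Nothing in the documents suggests such a pattern in a cohort open from 2010. Nor is a wide gap between favorable and intermediate risk supported; their shares on drug are close (19% and 15%) and so are their excesses.

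**Conclusion.** The point holds as a modest, conditional weakness. The plan handles censoring for TTD but not for its components, leaves the denominator open, and reports by strata whose completeness of follow-up is likely to differ.

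- **All patients as denominator:** each reason is understated by roughly 19%, 15% and 3% in relative terms (favorable, intermediate, poor), or about 9%, 5% and under 1% if starts ended in December 2016. This produces a gradient between groups even when their eventual reasons are identical.
- **Discontinuers as denominator:** 0 points if the mix is constant. If toxicity stops cluster early, about 1 to 3 points in favorable and intermediate risk and under 1 point in poor risk.

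All these sizes rest on PFS as a proxy for TTD, exponential or piecewise-constant hazards, uniform starts and no loss to follow-up. Heavy loss to follow-up or clustering of starts near the cut would enlarge them. No primary conclusion is threatened; this is a cheap improvement.

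**What to change.** In Section 7.7, add that the cumulative incidence of each discontinuation reason will be estimated by the Aalen-Johansen method, by IMDC group and by KPS, at fixed times (for example 6, 12 and 24 months). The other reasons are treated as competing events, and patients still on sunitinib are censored at the date last known on treatment.

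Keep the raw counts as a supporting table. State the denominator, and add a row per stratum for patients still on treatment or censored. The table then says plainly whether it describes all patients or only those who stopped.

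The cost is one or two sentences, a few lines of code and slightly more output. The TTD analysis already needs the start, stop and censoring dates, and Section 7.3 already lists the reason, so no new variable should be needed. Cumulative incidence at a fixed time also reflects how fast each group stops treatment, so it should be read beside the raw counts and not as a replacement for the mix of reasons among those who stopped. Like Kaplan-Meier, it assumes that censoring is unrelated to the risk of stopping.

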In addition to differences between IMDC prognostic risk groups, heterogeneity may exist within a risk group as well. Specifically, patients with IMDC intermediate risk group (defined as having 1 or 2 IMDC risk factors) may have different clinical outcomes depending on the number of risk factors. A retrospective analysis of six clinical trials examining sunitinib treatment for mRCC reported that among patients in the intermediate risk group, time interval less than 1 year from RCC diagnosis to targeted therapy was the most common risk factor as observed in 36% of patients with 1 risk factor alone or in combination with low serum hemoglobin as observed in 25% of patients with 2 risk factors. The study also found that patients with 1 risk factor had longer OS (25.6 vs. 16.3 months) and PFS (9.8 vs. 8.6 months), and greater ORR (39.5% vs. 31.8%) when compared to those with 2 risk factors. 12 These results are comparable to those from the retrospective analysis of sunitinib vs. interferon alfa phase III trial, where the median OS in patients with 1 risk factor was 28.2 months vs. 16.3 months in those with 2 risk factors. ORR was 33.3% (95% CI: 25.9, 41.5) in patients with 1 risk factor and 31.7% (95% CI: 20.3, 45.0) in those with 2 risk factors. Median PFS in intermediate risk group patients with 1 or 2 risk factors was 10.7 months. 10

Given the high interest to examine the effect of lines of treatments on clinical outcomes by IMDC prognostic risk group, Analysis Group, Inc. (AGI) will conduct a study to further understand the clinical outcomes in mRCC patients treated with sunitinib as first-line stratified by IMDC prognostic risk groups in real-world clinical practices using the IMDC database. This will provide contemporary benchmarks for outcomes and survival among mRCC treated with first-line sunitinib in the real world. Additionally, the clinical heterogeneity within the IMDC intermediate risk group and impact of individual IMDC prognostic risk factors will be explored.

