6. RESEARCH QUESTION AND OBJECTIVES

The study aims to address the following:

- 1. To describe patient demographic and clinical characteristics among all mRCC patients treated with sunitinib in first-line, stratified by IMDC prognostic risk score (ie, favorable, intermediate, and poor).
- 2. To characterize the following clinical outcomes in patients treated with sunitinib in first-line, stratified by IMDC prognostic risk groups and Karnofsky Performance Status (KPS).
 - OS;
 - Time to treatment discontinuation (TTD);
 - Reasons for treatment discontinuation:
 - Physician-assessed best response (objective response rate [ORR], progressive disease, stable disease).
- 3. To conduct a subgroup analysis assessing demographic and clinical characteristics and the following clinical outcomes among mRCC patients in the intermediate IMDC prognostic risk group, stratified by patients having only 1 IMDC risk factor versus 2 IMDC risk factors.
 - OS;
 - TTD;
 - Physician-assessed best response (ORR, progressive disease, stable disease).

[figure not shown]

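### Does the best-response summary in section 7.7 need a stated denominator, a row for unrecorded responses, and the full set of categories in the subgroup?

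*Combined protocol and SAP*

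**What the plan says.** Section 7.3 of the combined protocol and SAP defines the outcome: "Physician-assessed best response, defined as ORR (sum of partial response and complete response), progressive disease, and stable disease". Section 7.7 gives the analysis for the full cohort, stratified by IMDC risk group and by KPS: "Physician-assessed best tumor response (ie, objective response rate, stable disease, and progressive disease) to first-line sunitinib will be described using relative frequencies".

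Objective 3 in section 6, on intermediate-risk patients with 1 or 2 risk factors, lists "Physician-assessed best response (ORR, progressive disease, stable disease" and closes the bracket there. The matching subgroup paragraph of section 7.7 refers to "clinical outcomes (ie, OS, TTD, and ORR), stratified by patients having only 1 risk factor vs. 2 risk factors". It then applies the full-cohort methodology to demographic and clinical characteristics and to the same three named outcomes.

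Section 7.8 lists non-random missing data, and response assessment that varies between patients and practices, as limitations. Section 7.6 provides for correcting data-entry errors with the centers. Section 7.5 states that no power calculation was done because the main objectives are descriptive.

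**The concern.** A relative frequency needs a denominator. Two analysts could both follow section 7.7 and report different ORRs from the same data, one over all treated patients and one over patients with a recorded response. Discontinuation reasons, in the same list in section 7.3, have a residual category; best response has none. Sections 7.6 and 7.8 do not settle the matter, since one deals with data errors and the other only names the bias.

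Response by risk group is part of objective 2. If unrecorded responses were more common in one stratum than another, dropping those patients would raise ORR by different amounts and distort the contrast between strata. An ORR over assessed patients only, set beside an all-patient ORR from a trial, would also not compare like with like. In the 1 versus 2 factor subgroup, ORR reported alone would not show whether the categories account for every patient.

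**Working it through.** **1. Is there a design figure to reproduce?** No. The plan states no sample size, power or target for response. The checks below ask only how far the denominator could matter.

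**2. Effect of dropping unrecorded patients.** Let u be the share with no recorded response. Then ORR among recorded = ORR among all / (1 − u). The documents do not give u, so the values here are assumed.

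For a base rate, section 5 cites, from a re-analysis of the phase III trial of sunitinib against interferon alfa, "ORR was 33.3% (95% CI: 25.9, 41.5) in patients with 1 risk factor and 31.7"%, and then "31.7% (95% CI: 20.3, 45.0) in those with 2 risk factors". A search over n < 450 for counts whose rounded rate and exact (Clopper-Pearson) 95% limits match gives one solution each:
- 50/150 = 33.3% (25.86, 41.48)
- 19/60 = 31.7% (20.26, 44.96)

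Pooled: (50 + 19)/(150 + 60) = 69/210 = 32.9%. These counts are inferred, not stated.

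| assumed u | 32.9% / (1 − u) |
|---|---|
| 5% | 34.6% |
| 10% | 36.5% |
| 20% | 41.1% |

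Equal u in two strata leaves the ratio of their ORRs unchanged. Only unequal u distorts it.

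**3. Compared with sampling error.** Take 55% intermediate risk (a trial figure in section 5) of the 2,000 to 3,000 first-line patients in section 7.5: 1,100 to 1,650. The half-width is h = 1.96 × √(p(1 − p)/n), with p = 0.329. The shift equals h when u = h/(p + h).

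| n | h (points) | break-even u |
|---|---|---|
| 1,100 | 2.8 | 7.8% |
| 1,650 | 2.3 | 6.5% |
| 550 (cohort halved, assumed) | 3.9 | 10.7% |
| 825 (cohort halved, assumed) | 3.2 | 8.9% |

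So the denominator could outweigh sampling error at moderate u. Whether u reaches these values is unknown.

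**4. Would u differ by risk group?** An indirect argument uses the PFS medians in section 5: 14.1 months (favorable), 10.7 (intermediate), "and 2.4 months (95% CI: 1.1, 4.7) for favorable, intermediate, and poor risk groups, respectively". With constant hazards (assumed), the share progressed or dead by time t is 1 − 2^(−t/median). Assessment times of 6 weeks (1.38 months) and 12 weeks (2.76 months) are also assumed.

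| | favorable | intermediate | poor | poor/favorable |
|---|---|---|---|---|
| week 6 | 6.6% | 8.6% | 32.9% | 5.0 |
| week 12 | 12.7% | 16.4% | 54.9% | 4.3 |

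Moving only the poor-risk median over its interval (4.7 to 1.1 months) gives ratios of 2.8 to 8.9 at week 6 and 2.6 to 6.5 at week 12. More important, progression is itself a best-response category under section 7.3, so a patient recorded as progressing early is counted and not missing. The calculation cannot separate such patients from those who died unassessed. It says little about u.

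**5. Was the cited trial ORR over all patients?** The reconstruction totals 210. Section 5 reports that "of the 373 patients treated with sunitinib, there were 36% favorable, 55% intermediate, and 9% poor", and 55% after rounding means 373 × 0.545 = 203.3 to 373 × 0.555 = 207.0. The reconstructed total exceeds that by 3 to 7, so the two do not reconcile and cannot firmly show which denominator the trial used. The cited ORRs are also for intermediate risk split by factor count, whereas the side-by-side in section 7.7 concerns intermediate and poor risk combined. Section 7.7 does not say that ORR is among the outcomes compared there.

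**6. The subgroup wording.** Objective 3 names all three categories, section 7.3 defines best response as that set, and the subgroup paragraph carries over the full-cohort method. Read narrowly, that last sentence covers only the outcomes it names, so it does not by itself restore the other two categories. Read together, the three places most naturally make ORR a short label for best response.

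**The case for a change.** The strongest case for a change is that, in a descriptive study, the proportions are the result. Section 5 says the study is to supply benchmarks, and a benchmark ORR without its denominator is hard to use. Discontinuation reasons got a residual category and best response did not. The remedy would cost a few lines and one table row and would need no new variable.

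Much of this stands. The text is silent on the denominator, the lists for the subgroup do differ, and step 3 shows that the choice could exceed sampling error. What does not stand is the claim that the plan as written leads to a wrong or misleading result. The evidence for unequal loss across risk groups (step 4) and for a mismatch with the trial denominator (step 5) does not bear the weight put on it. What remains is a table convention that the plan leaves to the analyst and that the final report will have to show in any case.

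**Conclusion.** No change to the plan follows. The omission is a gap that analysts fill sensibly: a best-response table with N and the number not recorded in each stratum is normal practice, nothing in sections 7.3 or 7.7 prevents it, and it lets a reader compute ORR on either denominator. The difference between objective 3 and the subgroup paragraph is probably shorthand.

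The size is unknown. The figures of 34.6%, 36.5% and 41.1% rest on assumed shares of 5%, 10% and 20% and on a reconstructed base of 69/210. The break-even shares of 6.5% to 7.8% (8.9% to 10.7% if the cohort is halved) also rest on an assumed cohort size. Two things limit the consequence: no response hypothesis or power rests on the number, and the comparison with trials is qualitative. Section 7.8 already warns readers about missing data and inconsistent assessment. The conclusion depends on the report showing stratum totals and unrecorded counts. If it gave bare percentages, that would be a fault of the report.
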